8.1.5.2 St. George's Respiratory Questionnaire

The SGRQ is a 50-item PRO instrument developed to measure the health status of participants with airway obstruction diseases (Jones et al, 1991). The questionnaire is divided into 2 parts: Part 1 consists of 8 items that pertain to the severity of respiratory symptoms in the preceding 4 weeks, and Part 2 consists of 42 items related to the daily activity and psychosocial impacts of the individual's respiratory condition. The SGRQ yields a total score and 3 component scores (symptoms, activity, and impacts). The total score indicates the impact of disease on overall health status. This total score is expressed as a percentage of overall impairment, in which 100 represents the worst possible health status and 0 indicates the best possible health status. Likewise, the component scores range from 0 to 100, with higher scores indicative of greater impairment. Specific details on the scoring algorithms are provided by the developer in a user manual (Jones et al, 1991). A decrease of 4 units in the SGRQ total score has been established as the criterion for minimal clinically meaningful difference (MCID) (Jones 2005). St. George's Respiratory Questionnaire responders will be those with ≥ 4 unit decreases compared to baseline in SGRQ total score.

The SGRQ will be completed at home, using the ePRO, as per the SoA (Section 1.3 and Section 8.1.5).

8.1.5.3 Asthma Quality of Life Questionnaire for 12 Years and Older

The AQLQ(S)+12 is a questionnaire that measures the health-related quality of life experienced by asthma participants (Juniper et al, 1999; Juniper et al, 2005). The questionnaire comprises 4 separate domains (symptoms, activity limitations, emotional function, and environmental stimuli). Participants are asked to recall their experiences during the previous 2 weeks and to score each of the questions on a 7-point scale ranging from 7 (no impairment) to 1 (severe impairment). The overall score is calculated as the mean response to all questions. The 4 individual domain scores are the means of the responses to the questions in each of the domains. The responder definition for AQLQ(s)+12 is 0.5-point improvement from baseline.

The AQLQ(s)+12 will be completed at home, using the ePRO, as per the SoA (Section 1.3 and Section 8.1.5).

8.1.5.4 Asthma Impairment and Risk Questionnaire

The AIROTM is a PRO tool intended to identify patients 12 years and older whose health may

be at risk because of uncontrolled asthma. It has 10 questions that ask about respiratory symptoms, activity limitation, sleep, rescue medication use, social activities, exercise, difficulty controlling asthma, and exacerbations. All items have a yes/no response option and the tool is scored by summing the total number of 'yes' responses. This sum score is used to assess level of asthma control where: 0 to 1 is well controlled, 2 to 4 is not well controlled, and 5 to 10 is very poorly controlled. Thus, a higher score indicates worse control status.

The AIRQTM items have 2 different recall period: The first 7 impairment items are evaluated over the past 2 weeks and the last 3 risk items over the past 3 months or the past year. This study will use the past 12-month recall. The AIRQTM will be administered and completed on the ePRO by the participant, on-site as per the SoA (Section 1.3). The AIRQTM is estimated to take approximately 3 minutes to complete.

8.1.5.5 Sino-nasal Outcome Test

The Sino-Nasal Outcome Test 22 (SNOT-22) is a condition-specific HRQoL assessment which captures patient-reported physical problems, functional limitations, and emotional consequences of sino-nasal conditions (Piccirillo et al 2002, Hopkins et al 2009). Patient-reported symptom severity and symptom impact over the past 2 weeks are captured via a 6-point scale (0- No Problem to 5- Problem as bad as it can be). The total score is the sum of item scores and has a range from 0 to 110 (higher scores indicate poorer outcomes). A Minimal Importance Difference (MID) of 8.90 has been established for individual score change (Hopkins et al 2009).

The SNOT-22 will be completed only by participants with symptoms of chronic sinusitis (at screening), at home, as per the SoA (Section 1.3 and Section 8.1.5).

8.1.5.6 Participant Perception of OCS

This is a new survey to be developed for this study including one or 2 questions designed to learn about how participants feel about any change in their daily OCS dose (decrease or lack thereof) to be assessed, at home, as per the SoA (Section 1.3 and Section 8.1.5). Responses will be scored and change from baseline calculated.

8.2 Safety Assessments

Planned timepoints for all safety assessments are provided in the SoA (Table 1).

8.2.1 Hypothalamic-pituitary-adrenal Axis Evaluation

For all participants, HPA axis integrity will be evaluated after 4 weeks on 5 mg/day and prior to tapering down the OCS dose (for participants with baseline OCS doses equal to 5 mg/day, this will be assessed 4 weeks after the first dose of tezepelumab administration and before initiation of the OCS reduction phase).

First, a screening method with morning serum cortisol is done (8-9 am morning cortisol level), to evaluate whether the participant has:

- Normal cortisol levels (Table 9)
- Complete AI (Table 9).

Cortisol levels from the morning cortisol test that are below normal range and above the complete AI range are considered 'indeterminate' (Table 9), and require additional testing described below (for sites where tetracosactide is not available or not registered, please see Appendix M).

If the morning cortisol is in the indeterminate range, then the ACTH stimulation test is done within approximately 1 week (see Section 8.2.1.2 for details). The ACTH stimulation test is more specific than the morning cortisol test, and can determine whether the participant has:

- Normal cortisol levels: > 450 nmol/L (> 675 nmol/L for participants taking oestrogen-containing contraceptives)
- Complete AI: < 250 nmol/L (< 375 nmol/L for participants taking oestrogen-containing contraceptives)
- Partial AI: 250 to 450 nmol/L (375 to 675 nmol/L for participants taking oestrogen-containing contraceptives).

For morning serum cortisol and ACTH stimulation tests, hold OCS dose and other concomitant medications that could interfere with cortisol results as follows (see Section 6.5):

- The last OCS dose should be taken \geq 24 hours prior to testing
- Participants must not take ICS (or ICS/LABA if in single inhaler) treatment on the
 morning of the morning cortisol level/ACTH stimulation test (for participants taking a
 once-daily ICS/LABA formulation, eg, fluticasone furoate/vilanterol, participants must
 not take the treatment ≤ 24 hours prior to the morning of the morning cortisol
 level/ACTH stimulation test)
- If a participant requires a short course of macrolides, antivirals, or azoles, there must be a window of ≥ 1 week prior to the testing of cortisol levels.

The process will be as described in Figure 3.

[figure not shown]

Figure 3 Hypothalamic-pituitary-adrenal Axis Evaluation

Figure 3: For normal cortisol levels with concurrent signs/symptoms of AI, OCS down-titration should continue at a slower pace (1 mg Q4W). For complete AI identified via morning cortisol testing, refer to Section 8.2.1.1 for instructions on 3-month repeat testing. For partial AI or complete AI identified via ACTH stimulation test see Section 8.2.1.2 for instructions on 2-month or 3-month repeat testing respectively.

8.2.1.1 Morning Cortisol Test

The morning cortisol test will be done in all participants 4 weeks after reaching the 5 mg dose of OCS, and before further dose reductions. It is also done 3 months after a participant has completed a test indicating complete AI.

Serum samples for cortisol will be collected between 8 and 9 am and will be sent to a central laboratory for evaluation.

The following values will be used to define AI status for the morning cortisol test:

Table 9 Cortisol Status

AI status	SI units	Participants taking oestrogen- containing contraceptives
Normal	>350 nmol/L	>700 nmol/L
Indeterminate results	100 - 350 nmol/L	200 - 700 nmol/L
Complete AI	<100 nmol/L	<200 nmol/L

Once the results are available, the site will inform the participant of the results via telephone. For sites where tetracosactides are available, and depending on the result, the actions that will be implemented are as follows:

- If cortisol levels are within normal range and the participant does not exhibit any signs and/or symptoms of AI, the participant will continue OCS down-titration by 2.5 mg Q4W
- If cortisol levels are within normal range but the participant exhibits signs and/or symptoms of AI, then OCS down-titration should continue at a slower pace (1 mg Q4W).
- If cortisol levels are below the normal range and above the complete AI range (indeterminate result), then the participant will be instructed to maintain the current OCS dose and come back to the site within 1 week for an ACTH stimulation test (Section 8.2.1.2)
- If complete AI is confirmed, sites will inform participant that the OCS dose will remain the same without further reduction until there is evidence of recovery from the complete AI without worsening of asthma control. The morning cortisol test and associated clinical assessments (see Table 1) will be repeated 3 months later. After the repeat morning cortisol test, the site will inform the participant based on the results as follows:
 - If morning cortisol results indicate normal cortisol values, then reductions will be 2.5 mg Q4W, and the participant would subsequently move to maintenance at the OCS lowest possible dose
 - If morning cortisol results are indeterminate, then reductions will be delayed further, and the participant would return approximately 1 week later for an ACTH stimulation test:
 - o If normal result after ACTH stimulation (Table 10): reduce by 2.5 mg Q4W then move to maintenance at the lowest possible dose
 - If the result is partial AI after ACTH stimulation (Table 10): reduce by 1 mg Q4W then move to maintenance at the lowest possible dose
 - If complete AI result after ACTH stimulation (Table 10): OCS dose will not be reduced further, and participant will continue at the current OCS dose.
 - If morning cortisol tests again indicate complete AI at 3 months, the OCS dose will not be modified as this is the final attempt. The participant would move to maintenance at the current OCS dose.

For sites where tetracosactide is not available or not registered, please see Appendix M.

8.2.1.2 Adrenocorticotropic Hormone Stimulation Test

The tetracosactide (also known as Synacthen, Cortrosyn, or cosyntropin) ACTH stimulation test will be performed when morning cortisol levels are in the indeterminate range (for sites

where tetracosactide is not available or not registered, please see Appendix M).

Options for sourcing tetracosactide are provided below:

- Acquire Synacthen or Cortrosyn 250 mg for intravenous (IV) or intramuscular (IM) injection locally and submit invoices for reimbursement (preferred option, if possible).
- If the medication is available in your country but the site cannot directly acquire the medications, then Labcorp or AstraZeneca may arrange for delivery to the site.
- If the medication is available in your country, but delivery to the site is delayed, the site may request permission from Labcorp to use the alternative method described in Appendix M.
- Sites in countries where the medications are not registered must use the alternative method in Appendix M.

The following values will be used to define AI status for the ACTH stimulation test:

Table 10 ACTH Stimulation Status

AI status	SI units	Participants taking oestrogen- containing contraceptives
Normal	>450 nmol/L	>675 nmol/L
Indeterminate results	250 - 450 nmol/L	375 - 675 nmol/L
Complete AI	<250 nmol/L	<375 nmol/L

The sites will inform the participant of the morning cortisol results via phone call, and a visit will be scheduled within 1 week for the ACTH stimulation test.

An injection of the fast-acting ACTH stimulant will be given IV or IM. Serum samples for cortisol will be collected between 8 and 9 am and will be sent to a central laboratory for evaluation as follows: a blood sample for serum cortisol will be collected at 0 minutes (before IV or IM injection) and 30 minutes after the IV or IM injection. Peak cortisol response at 30 minutes will be selected to assess AI, and the OCS taper will follow the applicable scenario below:

• If a normal peak cortisol level is demonstrated at 30 minutes, the site will inform the participant via phone call, and the participant will continue OCS dose titration by 2.5 mg Q4W aiming for 0, and subsequently would move to maintenance at the lowest possible OCS dose

- If the peak cortisol level at 30 minutes is below the normal range yet above the level of complete AI (partial AI), or there are some signs/symptoms of AI or corticosteroid withdrawal syndrome, the site will inform the participant to continue OCS down-titration at a slower pace (1 mg Q4W). The morning cortisol test and associated clinical assessments (see Table 1) will be repeated 2 months later, as per the process described in Figure 3.
- If peak cortisol level at 30 minutes indicates complete AI, sites will inform participants that the OCS dose will remain the same without further reduction until there is evidence of recovery from the complete AI without worsening of asthma control. The morning cortisol test and associated clinical assessments (see Table 1) will be repeated 3 months later, as per the process described in Figure 3.

8.2.1.3 Management of Participants with Partial or Complete Adrenal Insufficiency Any participant showing partial or complete AI at initial or subsequent morning serum cortisol or ACTH stimulation test, will be educated for symptom awareness of adrenal suppression and use of steroid emergency cards.

In the absence of evidence of HPA axis recovery, participants should be instructed to carry some type of identification (worn around the neck or wrist or carried as a card) warning of their clinical status of corticosteroid dependence along with a medical report detailing the treatment measures needed, including IM hydrocortisone requirements. Corticosteroid supplementation is recommended during situations of stress (ie, fractures, surgery, trauma, labour, invasive dental procedures, severe systemic infections, major burns, and fever > 38.5°C).

Additionally, participants who have partial or complete AI at EOT (or sooner if deemed appropriate) should be followed up by an endocrinologist or other appropriate specialist.

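### Section 8.2.1.2: the symptom clause for the slower taper has no ACTH range, so complete AI with symptoms and a normal peak with symptoms each attract two conflicting instructions

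*Protocol*

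**What the plan says.** Section 8.2.1.2 applies after an indeterminate morning cortisol, at sites that can use tetracosactide. Its lead-in is: "Peak cortisol response at 30 minutes will be selected to assess AI, and the OCS taper will follow the applicable scenario below". Three bullets follow.

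1. Normal peak (above 450 nmol/L): "the participant will continue OCS dose titration by 2.5 mg Q4W aiming for 0". Symptoms are not mentioned.
2. Peak in the partial-AI range (250 to 450 nmol/L), "or there are some signs/symptoms of AI or corticosteroid withdrawal syndrome, the site will inform the participant to continue OCS down-titration at a slower pace". The pace is 1 mg every 4 weeks (Q4W), with a repeat morning cortisol after 2 months.
3. Complete-AI peak (below 250 nmol/L): "If peak cortisol level at 30 minutes indicates complete AI, sites will inform participants that the OCS dose will remain the same without further reduction". The retest is at 3 months. Symptoms are not mentioned.

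For participants on oestrogen-containing contraceptives the limits are 375 and 675 nmol/L.

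Other Protocol text on the same decisions:

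- Section 8.2.1.1, first morning cortisol: "If cortisol levels are within normal range but the participant exhibits signs and/or symptoms of AI, then OCS down-titration should continue at a slower pace".
- Section 8.2.1.1, ACTH result after a repeat morning test: "If complete AI result after ACTH stimulation (Table 10): OCS dose will not be reduced further".
- Note to Figure 3 (Section 8.2.1): "For partial AI or complete AI identified via ACTH stimulation test see Section 8.2.1.2 for instructions on 2-month or 3-month repeat testing respectively". The note also directs 1 mg Q4W for normal cortisol with AI symptoms.
- Synopsis Table B and Table 3: same dose in complete AI; 2.5 mg Q4W and no retest after a normal result. Neither table has a symptom entry.
- Tables 7 and 8: no reduction in complete AI, retest at 3 months.
- Section 8.1.2: once at 5 mg/day, investigators may choose 1 mg Q4W because of symptoms.
- Appendix M, the alternative method without tetracosactide: its second test has a row triggered by cortisol up to 350 nmol/L or by AI symptoms. That row then splits. A value of at least 250 nmol/L on either sample gives slow titration; below 250 on both gives delay.

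**The concern.** The lead-in assumes that exactly one scenario applies. Because the symptom limb of bullet 2 is joined by an unrestricted 'or', a symptomatic participant meets bullet 2 whatever the peak. Bullets 1 and 3 depend on the peak alone, so they still apply as well.

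What is at stake is participant safety. Sections 2.1 and 4.2 treat about 5 mg/day as the physiological dose, and Section 8.3.6 lists adrenal crisis as an event of special interest. A site acting on bullet 2 alone would take a symptomatic participant with complete AI below that dose. A site acting on bullet 1 alone would taper a symptomatic participant with a normal peak in steps 2.5 times as large as the Figure 3 note directs (2.5 mg against 1 mg, both Q4W). Section 2.1 describes AI symptoms as often nonspecific, with fatigue and nausea as examples, so the symptom trigger is easily met.

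**Working it through.** The plan states no figure to reproduce; the check is of the rules themselves.

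**Step 1. Apply the three bullets literally to each ACTH class, with and without symptoms.**

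| ACTH peak (nmol/L) | Symptoms | Bullets met | Action |
|---|---|---|---|
| < 250 (complete AI) | no | 3 | no reduction, retest at 3 months |
| < 250 (complete AI) | yes | 2 and 3 | 1 mg Q4W, retest at 2 months; or no reduction, retest at 3 months |
| 250–450 (partial AI) | no | 2 | 1 mg Q4W, retest at 2 months |
| 250–450 (partial AI) | yes | 2 | 1 mg Q4W, retest at 2 months |
| > 450 (normal) | no | 1 | 2.5 mg Q4W |
| > 450 (normal) | yes | 1 and 2 | 2.5 mg Q4W; or 1 mg Q4W, retest at 2 months |

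Two of six cells give two different actions. In the last row, bullet 2's retest also disagrees with Tables B and 3, which require none after a normal result.

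**Step 2. Compare the parallel rules.** Section 8.2.1.1 limits its symptom rule to normal cortisol, which prevents both overlaps. The Appendix M second test supplies only the lower limit:

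- Below 250 nmol/L on both samples, with or without symptoms, gives delay only. There is no conflict.
- Sample 2 above 350 nmol/L with symptoms meets the > 350 row (2.5 mg Q4W). It also meets the symptom-triggered row, whose slow branch (1 mg Q4W) applies because one sample is at least 250. The overlap remains.
- In the fourth test the > 350 row already provides 1 mg Q4W when symptoms are present, so the taper rates agree.

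**Step 3. Hypothetical dose difference.** Assume 5 mg/day when the result arrives, a first step at once, a second step 4 weeks later, and totals over 56 days.

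- Complete AI with symptoms:
  - bullet 2: 28 × 4 + 28 × 3 = 196 mg, with 3 mg/day just before the 2-month retest
  - bullet 3: 56 × 5 = 280 mg
  - difference: 280 − 196 = 84 mg; 84/280 = 30% less under bullet 2
- Normal peak with symptoms:
  - bullet 1: 28 × 2.5 + 28 × 0 = 70 mg, with 0 mg/day from week 4
  - bullet 2: 196 mg
  - difference: 196 − 70 = 126 mg; 126/196 = 64% less under bullet 1

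**Step 4. Check the repair.** Limit the symptom clause to a normal peak and bullet 1 to a normal peak without symptoms. Each of the six cells then meets one bullet: complete AI with symptoms meets only bullet 3, and a normal peak with symptoms meets only bullet 2.

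**The case against.** The strongest reply is that the rest of the protocol already settles both cases. For complete AI, bullet 3 names the condition, and Tables B, 3, 7 and 8, Section 8.2.1.1 and Appendix M all give no reduction. Section 4.1 bases the decision on the ACTH result. Bullet 2 speaks of a slower pace, which presupposes a taper to slow, and its laboratory limb lies above the complete-AI range. For a normal peak with symptoms, the Figure 3 note directs 1 mg Q4W and Section 8.1.2 permits it. Section 8.2.1.3 adds symptom education, emergency cards and specialist follow-up for anyone with partial or complete AI. The Figure 3 flowchart, to which bullets 2 and 3 refer, is not shown in the text reviewed and may set out the order.

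Most of this stands. It fixes the intent and makes it likely that most sites would not reduce in complete AI. It does not remove the contradiction:

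- The tables have no symptom entry, so a site with a symptomatic participant would look to 8.2.1.2. The Figure 3 note sends readers there for ACTH retest instructions, while 8.2.1.2 refers back to Figure 3.
- For a normal peak with symptoms, the other texts support the slower rate but do not settle the retest: 2 months in bullet 2, none in Tables B and 3.

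A reader might infer that the protocol intends to taper symptomatic participants through complete AI. The documents do not support that, because every other statement on complete AI says the opposite. A reader might also take Appendix M as showing the missing limit at both ends; it does so only at the lower end.

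**Conclusion.** The contradiction is real but narrow, and it should be corrected. One safety dosing rule gives two actions in two of its six cells, and on one literal branch the action is wrong: tapering in complete AI. The overlap follows from the wording alone. Whether it would mislead a site is less certain, because the intended actions can be recovered elsewhere and the flowchart could not be checked.

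The complete-AI case needs an indeterminate morning cortisol, then a complete-AI peak, plus symptoms. The documents do not say how many participants that would be. The differences of 84 mg and 126 mg illustrate what each bullet implies. The first arises only if a site follows bullet 2 over bullet 3 and the tables. The second arises only if a site follows bullet 1 over bullet 2 and the Figure 3 note, without using the discretion in Section 8.1.2. A reader might go on to infer bias in the OCS endpoints; nothing in the documents supports that, and no effect on any endpoint or statistical figure is claimed.

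**What to change.** 1. Bullet 2: apply it to partial AI, or to a normal peak with signs or symptoms of AI or corticosteroid withdrawal syndrome.
2. Bullet 1: limit it to a normal peak without such signs or symptoms.
3. Bullet 3: in complete AI, no OCS reduction with or without symptoms, and a retest at 3 months. State that an increase is allowed if clinically needed. SAP Section 3.3 counts doses given for AI symptoms and adrenal crisis as maintenance OCS, so the wording should not appear to bar them.
4. Choose one retest interval (or none) for a normal peak with symptoms, and make bullet 2, Table 3 and synopsis Table B agree. Changing only Table 3 would create a new mismatch.
5. Appendix M, second test, > 350 nmol/L row: 2.5 mg Q4W without symptoms and 1 mg Q4W with symptoms, as in the fourth test.
6. Check that the Figure 3 flowchart shows the same order.

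The cost is a few reworded lines and a short note to sites. No procedure, visit or analysis changes.
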